# Purpose and Rationale

The purpose of this study is to examine the impact of applying a menthol-based gel to the skin on human thermoregulation and thermal perception during exercise in the heat.

Transient receptor potential (TRP) channels are a family of membrane proteins evolved to interpret environmental stimuli through ion channels. One of these channels, the TRP melastatin 8 (TRPM8), is responsible for the sensation of innocuous cool temperatures and it might be responsible for noxious cold temperatures [1,2]. When applied topically, menthol acts upon a cold transduction enzyme to decrease the thermal sensitivity of TRPM8. This decreased thermal sensitivity allows activation of TRPM8 at warmer temperatures, mimicking a cool sensation in warm environments. This cool menthol feeling is used widely in everyday commercial products, but most popular when used as an analgesic in medicated pain-relieving gels/creams.

Current recommendations suggest menthol can be used as an ergogenic aid resulting in an improved performance within heated environments [1]. By decreasing thermal sensitivity of TRPM8 receptors, menthol exerts a physiological response that is perceived as external cooling. The most salient response is an increase in heat conservation, resulting in a reduced exercise capacity due to fatigue associated with a rise in core body temperature [3]. It seems

the application and concentration strength of menthol application to the skin may be the most obvious influential factors. As such, researchers have used proprietary menthol solutions with varying intensities (0.05- 10%) [1], yet, to our knowledge, no one has investigated widely available, over-the- counter products. Indeed, the translation from proprietary formula to over-the-counter application is unknown. Furthermore, it is unclear if currently available menthol products may also aid in performance. This incongruence requires further investigation into the effect of menthol on exercise performance.

### **Participants**

12-15 subjects, age 19 to 45 years, will be needed to complete the study. Nineteen is the age of majority at the study site. The 2022 physical activity readiness questionnaire (PARQ) requires that adults aged >45 who are not accustomed to regular physical activity seek professional consultation prior to beginning physical activity. Thereby, keeping an age range of 19-45 ensures that the participants will be of consenting age and cleared for physical activity participation.

#### Research Plan

Three experimental visits to the laboratory will be conducted. All visits will take place at the University of Nebraska at Omaha, Exercise Physiology Laboratory. Visit 1 will consist of the physical activity readiness questionnaire (PARQ), adverse reaction to BioFreeze, and body composition (hydrostatic weigh, bioelectrical impedance). Visits 2 and 3 will be separated by 7-14 days, randomized, and counterbalanced for experimental (BioFreeze) and control (hypoallergenic cream) trials. Both the experimental and control visits will follow the same protocol.

Participants will arrive following an overnight fast state while also refraining from strenuous activity, alcohol consumption, tobacco use, and recreational drugs for the previous 24-hour period. During these visit researchers will apply BioFreeze using a gloved hand from shoulder to wrist and mid-thigh to ankle (areas outside of the clothing). A hypoallergenic cream will be applied during the control visit.

Exercise will consist of 30 min of moderate intensity treadmill walking (3.5 mph at 5% grade) within a heated temperature/humidity-controlled chamber (38°C, 60% relative humidity).

Participants will be weighed before, and after completion of the exercise calculate sweat rate. Prior to the exercise session, participants will sit for 5 min in an ambient room temperature environment as a baseline. During baseline and during the exercise core temperature, skin temperature, laser doppler blood flow, galvanic skin response, and heart rate will be collected continuously. Sweat patches will be adhered to the forehead during exercise at minute 10 for collection of sweat composition over the next 10-20 minutes.

Thermal perception using the ASHRAE scale (cold to hot) will be assessed pre and during exercise.

### VISIT 1

Visit 1 will take approximately 1 hour. Informed consent will be given. Participants will then complete the physical activity readiness questionnaire (PARQ) to be cleared for physical activity. Participants will have a small amount of the BioFreeze cream applied to a small area of the forearm (~2 x 2 in) to test for any adverse reaction over a period of 15 minutes. This initial skin reaction test is not a part of the research protocol. Then, resting blood pressure will be taken. Those without a reaction, and a resting blood pressure lower than 140/90, will have height, weight, and body fat composition measured. Height and weight will be measured using a medical scale and stadiometer, respectively. Body fat will be assessed with hydrostatic weighing using an electronic load cell-based system (Exertech, Dresbach, MN) correcting for residual lung volume or via a bio-electrical impedance analyzer (InBodyUSA, Cerritos, CA).

## VISITS 2 AND 3

Visits 2 and 3 will take approximately 2 hours each. Upon arrival at the lab, a nude body weight will be collected with the subject in a private room. While still in the room, subjects will self-insert a rectal thermistor 12-15 cm beyond the anal sphincter and don a chest strap heart rate monitor. After dressing in their exercise clothing, subjects will exit the private room so that chest, forearm, and calf thermistors can be adhered to the skin with tape.

Laser doppler flow (forearm and or/finger) will be adhered with tape and galvanic skin response (fingers) will be adhered using Velcro straps to the skin. Measuring instruments will be recorded using an integrated digital to analog converter (ADInstruments, Colorado Springs, CO).

Following instrumentation, subjects will sit for 5 minutes as a baseline in a temperate environment. Immediately after, a researcher with gloved hands will topically apply BioFreeze or the control hypoallergenic cream from the shoulder to wrist and mid-thigh to ankle. Subjects will then enter the heat chamber (38°C, 60% relative humidity) and immediately begin a 30-minute walk on a treadmill (3.5 mph, 5% grade). Subjects will be intermittently asked to hold their arm steady for laser doppler flow collection (10, 20, 30 minutes). Subjects will also briefly pause at minute 10 in order to adhere an absorbent patch to their forehead for sweat collection over the following 10-20 minutes. Thermal perception using the ASHRAE scale (cold to hot) will be assessed pre and during exercise. After 30 minutes of walking, subjects will exit the chamber for removal of all skin and finger sensors. Subjects will then reenter the private room, remove their own rectal thermistor with gloved hands, and then a final nude body weight will be recorded after toweling off.

The rectal thermistor will measure core temperature. The heart rate monitor will measure the beats of the heart. Skin thermistors will measure the temperature of the skin surfaces. Laser doppler flow measure the relative units of blood flow velocity.

Galvanic skin response measures skin conductivity changes as individuals begin to sweat. Sweat is collected for assessment of sweat composition. Thermal perception is assessed for individual perception surrounding the temperature of the ambient environment. Nude body weight is measured to calculate sweat rate.

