#### **Abstract**

The purpose of this study is to examine the human thermoregulatory impact of applying a commercially available menthol gel (BioFreeze) to the skin prior to moderate intensity walking under heated conditions. Eligible participants will be aged 19-45 years, have no previously known adverse reactions to menthol (active ingredient in BioFreeze) based upon a self-report, no adverse reactions to BioFreeze as determined through gel application to a small forearm area, and cleared for physical activity via the 2022 Physical Activity Readiness Questionnaire (PARQ). There will be a total of 3 experimental visits to the laboratory. Visit 1 will test for adverse BioFreeze reaction by applying a small amount of gel to the forearm (~2 x 2 in). Anthropometric and body composition data will also be collected at this time. Visits 2 and 3 will consist of 30 min of treadmill walking at a moderate pace (3.5 mph, 5% grade) under hot conditions (38°C, 60%RH). Visits 2 and 3 will be randomized and counterbalanced for BioFreeze or a hypoallergenic gel (control) application. Gels will be applied to areas commonly exposed during outdoor activity in warm conditions (shoulder to wrist, mid-thigh to ankle). Accordingly, participants will wear shorts and a tank top shirt during exercise. Core temperature, skin temperature, galvanic skin response, laser doppler blood flow, and heart rate will be continuously recorded throughout the exercise bout via an integrated analog to digital converter. Sweat will be collected during exercise using commercially available absorbent patches. Thermal sensation will be assessed throughout exercise via the ASHRAE thermal sensation likert scale (cold to hot). Lastly, nude body weight will be recorded pre and post exercise for sweat rate determination. The BioFreeze and control trials will be separated by a 7 to 14 day washout period.

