# Statistical Analysis

#### Recruitment

Previous exercise research suggests that the difference in response of matched pairs is normally distributed with a standard deviation of 0.86. If the true difference of the mean response of matched pairs is 0.75, we will need to complete 12 experimental trials for each condition to be able to reject the null hypothesis that this response difference is zero with a power of 0.8. The Type I error probability associated with this test of the null hypothesis is 0.05.

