#### Interventions

A repeated measures two-way ANOVA (Time x condition) will be used for the dependent variables. If the F-ratio values are found to be significant, a Fisher's Least Significant Difference post hoc analysis will be conducted. A type I error probability of < 5% will be considered significant (p< 0.05). All data will be analyzed using a combination of Microsoft Excel and the Statistical Package for the Social Sciences (SPSS).

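### Visit order is randomised and counterbalanced, but the planned ANOVA has no order term, so any shift between visits 2 and 3 inflates the error for the condition comparison

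*Combined protocol and SAP*

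**What the plan says.** The Abstract and the Research Plan both fix the order by design. The Abstract has "Visits 2 and 3 will be randomized and counterbalanced for BioFreeze or a hypoallergenic gel (control) application", and the Research Plan has "Visits 2 and 3 will be separated by 7-14 days, randomized, and counterbalanced for experimental (BioFreeze) and control (hypoallergenic cream) trials". The Abstract adds: "The BioFreeze and control trials will be separated by a 7 to 14 day washout period".

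The analysis text under Statistical Analysis, Interventions, is short: "A repeated measures two-way ANOVA (Time x condition) will be used for the dependent variables". Fisher's LSD follows a significant F-ratio. No section adds order, sequence, period or visit to the model. The plan does not define its time factor, but laser Doppler readings at 10, 20 and 30 minutes and a seated baseline make it read as time within a session, not as visit.

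Visit 1 involves no walk in the heat chamber: "Visit 1 will consist of the physical activity readiness questionnaire (PARQ), adverse reaction to BioFreeze, and body composition (hydrostatic weigh, bioelectrical impedance". Visit 2 is therefore each participant's first such walk in this study, and visit 3 the second.

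**The concern.** In a two-visit crossover, anything that changes between the first and second test session adds to the treatment difference in one order and subtracts from it in the other. Counterbalancing removes this from the average difference when the orders are equal. It does not remove it from the spread of the differences, and that spread is the error against which condition is tested. The design balances a nuisance that the analysis then leaves in the noise.

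A shift is plausible here, because the hot chamber, the treadmill task and the self-inserted rectal probe are all met first at visit 2, and one outcome is a self-rated thermal scale. The stake is sensitivity in a study of about 12 pairs, not false positives. The comparisons affected are the condition main effect, BioFreeze versus control at a single time point, and outcomes obtained once per visit (for example, "Nude body weight is measured to calculate sweat rate").

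**Working it through.** **Inputs.** From Statistical Analysis, Recruitment: true paired difference 0.75, SD of paired differences 0.86, 12 pairs, power 0.8, alpha 0.05 (taken as two-sided; the plan does not say). From Participants: 12 to 15 completers. Assumed: a 6/6 split at n = 12, and a visit shift s between 0 and 0.86 in the units of the paired difference, because the documents give none.

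**1. The plan's own figure.** For a paired t-test the noncentrality is 0.75/0.86 × √12 = 0.872 × 3.464 = 3.02. With 11 df, power is 78.5%; at n = 13 it is 82.3%. The stated 12 pairs is reproduced to within one pair.

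**2. What a shift does.** Let τ be the treatment difference and s the change from visit 2 to visit 3. The BioFreeze-minus-control difference has mean τ + s in those taking control first (n1) and τ − s in those taking BioFreeze first (n2). Ignoring order:

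- bias of the mean difference = s × (n1 − n2)/n
- expected variance of the differences = 0.86² + s² × 4·n1·n2/(n(n − 1))

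At 6/6 the bias is 0 and the multiplier of s² is 144/132 = 1.091. For s = 0.43 the variance is 0.7396 + 0.1849 × 1.091 = 0.941, so the working SD is 0.970 instead of 0.86.

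With order in the analysis, the estimate is the plain average of the two order-group means, the error is the pooled within-order SD (0.86), and the df are n − 2.

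**3. Power and type I error if 0.86 excludes the shift** (n = 12, 6/6; exact noncentral t at s = 0, otherwise simulation with 400,000 runs per case):

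| Shift s | SD without order term | Power without | Power with | Type I error without |
|---|---|---|---|---|
| 0 | 0.860 | 78.5% | 77.7% | 5.0% |
| 0.1 | 0.866 | 78.0% | 77.7% | 4.8% |
| 0.215 | 0.889 | 76.3% | 77.6% | 4.4% |
| 0.43 | 0.970 | 70.2% | 77.8% | 3.0% |
| 0.86 | 1.244 | 46.3% | 77.7% | 0.7% |

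With the order term, type I error is 5.0% throughout. The two analyses break even at a shift of about 0.14 to 0.15.

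**4. If 0.86 already contains the shift.** The residual SD is then √(0.86² − s²): 0.833 at s = 0.215 and 0.745 at s = 0.43. Power without and with the order term is 78.9% and 80.2%, then 80.5% and 88.0%. Nothing is lost against plan, but adjustment still gains.

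**5. Unequal orders, s = 0.43.** The bias is 0.43 × 1/13 = 0.033 at 7/6, 0.43 × 1/15 = 0.029 at 8/7 (both about 4% of 0.75), and 0.43 × 2/12 = 0.072 at 7/5. Unadjusted type I error is 3.6% at 7/5 and 5.5% at 8/4, so even a marked imbalance barely moves it above 5%.

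**6. Time x condition.** A shift that is the same throughout the session drops out of within-session changes. In a simulation with 12 participants, four time points and a constant shift of one within-person SD, the interaction test kept a type I error of 5.0% to 5.2% with or without the order factor.

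**The case against.** The strongest reply is that the loss depends on a quantity the documents never give. The largest assumed shift, 0.86, equals a full SD and exceeds the planned treatment effect, so 46.3% marks an extreme and not an expectation. Below about 0.15 the order term costs a little power. The Recruitment text says only that "the difference in response of matched pairs is normally distributed with a standard deviation of 0.86"; if that SD came from repeated visits analysed without order, it already includes any shift and power is not below plan. The gel goes on after the seated baseline, so if baseline is a level of time, a gel effect would show in Time x condition, which a constant shift does not touch. Randomised order, the same procedures at both visits and a controlled chamber already protect against bias. Finally, the figures come from a paired t-test on one unnamed response, not from the multi-time ANOVA that is planned.

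All of this stands as a limit on size. None of it supplies an order term or shows that a shift is absent. The condition main effect, same-time contrasts and sweat rate remain exposed. For once-per-visit outcomes and the condition main effect, the test reduces to one difference per participant, so the paired calculation is the relevant one.

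**Conclusion.** The concern holds as a point of efficiency, not of validity. The plan randomises order and then leaves it out of the model. If there is a visit shift, the condition comparison is less sensitive than the design allows and, with equal orders, conservative. The gain from adjustment is nil or slightly negative for a shift below about 0.15, about 1 power point at 0.215, and 7 to 8 points at 0.43, whichever way the 0.86 is read. Bias is zero with equal orders and small at 7/6 or 8/7, which can arise because "12-15 subjects, age 19 to 45 years, will be needed to complete the study" allows odd numbers.

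These sizes rest on the assumed shift, a two-sided test and a near-equal split. Time x condition is unaffected unless the shift varies over the session. The point does not concern carryover, which an order term would not resolve.

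**What to change.** Add one sentence to Statistical Analysis, Interventions, before the data are examined, because adding order after seeing a visit effect would be a data-driven choice:

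- Enter order (BioFreeze first or control first) as a between-subjects factor in the SPSS repeated-measures ANOVA. The condition x order term then takes up the visit effect.
- Report the BioFreeze-minus-control difference as the equally weighted mean of the two order groups, with its confidence interval. Analyse once-per-visit outcomes the same way.
- If a mixed model is used instead, include condition, time, condition x time and visit as fixed effects, with random effects for participant and for participant-by-visit. A participant effect alone is not adequate: with 12 participants, four time points and no treatment effect, it gave type I errors for condition of 13.7%, 27.7% and 40.6% when participant-by-visit variation made up an assumed 20%, 50% and 80% of within-person variance. The ANOVA with the order factor stayed at 4.9% to 5.0%.

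**Cost.** No new data. The condition test loses one error df (11 to 10 at n = 12). With no visit effect that costs under 1 power point at 6/6, about 2 points at 7/5 (78.5% to 76.6%) and about 6 points at 8/4 (78.6% to 72.9% in simulation), so near-equal orders among completers are worth protecting. In the time strata the factor costs T − 1 error df for T time points, for example 33 to 30 with four.

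### The Visit 1 skin test that decides eligibility covers BioFreeze only and is read for 15 minutes, with no later check described before either product goes on the limbs

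*Combined protocol and SAP*

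**What the plan says.** The Abstract sets two reaction-related eligibility conditions. One is history: "no previously known adverse reactions to menthol (active ingredient in BioFreeze) based upon a self-report". The other is the skin test: "no adverse reactions to BioFreeze as determined through gel application to a small forearm area".

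The Visit 1 text describes the test as a patch of BioFreeze, about 2 x 2 inches, on the forearm, "to test for any adverse reaction over a period of 15 minutes". The result is acted on: "Those without a reaction, and a resting blood pressure lower than 140/90, will have height, weight, and body fat composition measured". The same paragraph also states: "This initial skin reaction test is not a part of the research protocol".

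For the comparator, the Research Plan says "A hypoallergenic cream will be applied during the control visit". No skin test of that cream is described. At Visits 2 and 3 a researcher is to "topically apply BioFreeze or the control hypoallergenic cream from the shoulder to wrist and mid-thigh to ankle", after which the participant enters the chamber and walks for 30 minutes. Visits 2 and 3 are 7 to 14 days apart; no interval between Visit 1 and Visit 2 is stated. The first step described at Visits 2 and 3 is the nude body weight, and no question about reactions and no inspection of the test site is mentioned.

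**The concern.** The test decides who may go on to large-area application, yet two kinds of reaction lie outside what it can detect. It cannot reveal a reaction to the control cream, because that cream is not applied. It cannot reveal a BioFreeze reaction that first appears after 15 minutes, because no later reading is described. A participant with either could meet every written condition and then have the product put on both arms and most of both legs.

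The first thing at stake is participant safety. The second is the data from an affected participant: the forearm and calf thermistors, and the laser Doppler probe when it is placed on the forearm, sit on treated skin, and a completed pair could be lost.

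The status of the test is a separate matter. The Abstract treats its result as an eligibility condition and the opening of the Research Plan lists it as content of one of three experimental visits, but the Visit 1 text places it outside the research protocol. It is therefore unclear whether a reaction to the patch is to be recorded as study information.

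**Working it through.** No figure in the plan depends on the skin test, so the main check is a comparison of what is screened with what is later applied.

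| Item | Screened | Later exposure |
|---|---|---|
| BioFreeze, known reaction | Yes, self-reported menthol history (Abstract) | Both arms; legs from mid-thigh down |
| BioFreeze, first reaction within 15 minutes | Yes, patch test (Visit 1) | Same |
| BioFreeze, first reaction after 15 minutes | No reading described | Same; the walk alone lasts 30 minutes |
| Control cream, any reaction | No test described; described as hypoallergenic | Same area, same walk |

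The design is a crossover, so each participant meets all of the exposures in the right-hand column. Laser Doppler is read at 10, 20 and 30 minutes of the walk. The product goes on before the walk starts, so the 20- and 30-minute readings fall more than 15 minutes after application.

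**How often this could arise.** The plan gives no reaction rate. For an assumed per-person rate r of a reaction the screening misses, the chance of at least one such participant among n is 1 − (1 − r)^n. For example, with r = 0.01 and n = 12, 1 − 0.99^12 = 0.114. The Participants section plans 12 to 15 people.

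| Assumed r | n = 12 | n = 15 |
|---|---|---|
| 0.5% | 5.8% | 7.2% |
| 1% | 11.4% | 14.0% |
| 2% | 21.5% | 26.1% |
| 5% | 46.0% | 53.7% |
| 10% | 71.8% | 79.4% |

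The rates are illustrative; nothing in the plan favours one row over another.

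**What a lost pair would cost.** The Recruitment paragraph of the Statistical Analysis gives a paired difference of 0.75, SD 0.86, alpha 0.05, power 0.8 and 12 trials per condition. The standardised difference is 0.75 / 0.86 = 0.872. With a two-sided paired t-test (sidedness is not stated, so this is assumed), the noncentral t distribution gives power 0.785 at 12 pairs and 0.823 at 13, so the plan's 12 is reproduced to within one pair. Dropping from 12 pairs to 11 takes power from 0.785 to 0.741, a loss of 0.044. Dropping from 15 to 14 takes it from 0.881 to 0.854, which still exceeds the target.

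**The case against.** The strongest reply is that the screening is reasonable for a short study. The active product is the one tested, known menthol reactors are excluded, and the comparator is described as hypoallergenic. This narrows the gap considerably. It does not close it: the history question concerns menthol only, and a description of the cream is not a test of the participant.

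It can also be said that a re-check may happen in practice. Visit 1 lasts about an hour and other measurements follow the patch. At Visits 2 and 3 staff tape a sensor to the forearm and apply the product by hand. Consent pages are not available to this review and may ask participants to report reactions. This stands. The plan is silent on a second look; it does not rule one out.

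Three stronger readings are tempting, and the plan does not support them.

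- A reader might infer that testing one product only biases the comparison. The same screened people receive both products, so the screening creates no imbalance between conditions. A reaction under one product could shift that person's local readings in that condition, but no frequency or size is given from which to show a bias.
- A reader might infer risk from the ratio of treated to tested area. A 2 x 2 inch patch is 5.08 cm x 5.08 cm = 25.8 cm². If 25% to 40% of a body surface of 1.6 to 2.0 m² were treated (assumed), that is 4,000 to 8,000 cm², or 155 to 310 times the patch. This describes extent of exposure. It says nothing about how often reactions occur.
- A reader might infer that contact with the patch is limited to 15 minutes. The plan gives 15 minutes as the observation period and does not say that the gel is then removed.

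Finally, the sentence placing the test outside the research protocol can be read as meaning that it is screening and not study data. That is possible, but the text does not say so.

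**Conclusion.** The point holds in a limited form. The test is an eligibility condition, it covers one of the two products, it is read over 15 minutes, and no later reading or question before application is described. The remaining gap is first-time BioFreeze reactions appearing after 15 minutes and reactions to the control cream. Its size cannot be established from the plan; the 11% to 46% chance of at least one case among 12 rests wholly on an assumed rate of 1% to 5%. The effect on power is small: one lost pair matters if only 12 are recruited and can be absorbed if 15 are. No bias in the paired contrast is demonstrated.

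This is an inexpensive improvement, chiefly for participant safety, and not a flaw that threatens the analysis. The conflict over the status of the test is plain on the face of the text and needs resolving whatever is decided about the rest.

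**What to change.** 1. At Visit 1, during the same 15 minutes, apply the control cream to a second small forearm patch and read both. The existing criterion names BioFreeze only, so the eligibility text should also say how a reaction at the control patch counts.
2. On arrival at Visit 2, before any product is applied, ask about and look for any reaction since Visit 1, record the answer and the finding, and assess them against the existing eligibility criterion. As no Visit 1 to Visit 2 interval is stated, record the date of each visit so that the length of follow-up of the patches is known.
3. Reconcile the Visit 1 sentence on the status of the test with the Abstract and the opening of the Research Plan. It is for the sponsor to decide which description is intended; the text should then say whether reactions to the patch are recorded as study information.

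The cost is a small amount of control cream, a few minutes of staff time and a text edit, with no extra visit or chamber time. The downside is a possible extra screen failure. The 15-minute reading itself is unchanged; the Visit 2 check is what picks up later reactions.

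### Does taping the sensors on before the gel mean that blood flow and skin temperature are never read on treated skin?

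*Combined protocol and SAP*

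**What the plan says.** The Visits 2 and 3 text in the Research Plan describes instrumentation first. Skin sensors go on so that "chest, forearm, and calf thermistors can be adhered to the skin with tape", and for blood flow "Laser doppler flow (forearm and or/finger) will be adhered with tape". Then: "Following instrumentation, subjects will sit for 5 minutes as a baseline in a temperate environment". Directly after the baseline a researcher is to "topically apply BioFreeze or the control hypoallergenic cream from the shoulder to wrist and mid-thigh to ankle". Participants next enter the chamber "and immediately begin a 30-minute walk on a treadmill". Removal is described once: "After 30 minutes of walking, subjects will exit the chamber for removal of all skin and finger sensors".

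On recording, the Research Plan states: "During baseline and during the exercise core temperature, skin temperature, laser doppler blood flow, galvanic skin response, and heart rate will be collected continuously". The Visits 2 and 3 text adds that the arm is held still for laser Doppler readings at 10, 20 and 30 minutes, and explains the signal as follows: "Laser doppler flow measure the relative units of blood flow velocity".

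Nothing says whether product goes over, around or under a sensor. Nothing says which laser Doppler site is used, or whether forearm and finger are analysed separately.

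**The concern.** The Purpose and Rationale section rests the study on menthol acting at cold receptors in the skin. Blood flow and skin temperature are the two measures that might show a local effect of that action. Following the written order literally, a forearm probe already covers its patch of skin when product is spread, and a finger probe is outside the application area. The forearm and calf thermistors are in the first position and the chest thermistor is in the second.

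If that is what happens, a null result on either measure is ambiguous: the gel may leave treated skin unchanged, or treated skin may not have been measured. No later analysis could separate the two. If staff instead lift and re-tape the probe, baseline and exercise flow values, which are in relative units, come from two placements, and the placement change adds noise to the Time and Time x condition terms of the planned ANOVA.

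**Working it through.** **Plan figures.** The only sizing figures are in the Recruitment section: mean paired difference 0.75, standard deviation 0.86, 12 trials per condition, power 0.8, type I error 0.05. Taking the test as two-sided (an assumption), the normal approximation gives n = (0.86 × (1.960 + 0.842) / 0.75)² = 10.32, so 11. Exact power of the paired t-test is 0.785 at n = 12 and 0.823 at n = 13. The stated 12 is reproduced closely enough. These figures are not tied to blood flow or skin temperature, so they cannot size the present point. What remains is a reading of sites and order.

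**Sites against the application area and the order of steps.**

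| Sensor | Site | Within application area? | Attached before product? |
|---|---|---|---|
| Laser Doppler | forearm | yes | yes |
| Laser Doppler | finger | no | yes |
| Thermistor | forearm | yes | yes |
| Thermistor | calf | yes | yes |
| Thermistor | chest | no | yes |
| Galvanic skin response | fingers | no | yes |
| Sweat patch | forehead | no | no (minute 10 of the walk) |

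The table confirms the order. It also shows that measuring away from the gel is usual in this study: the chest, finger and forehead sites are all outside the application area. At the forearm and calf the surrounding skin is treated, and only the small patch under each sensor is in doubt.

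**Does the text exclude lifting and re-taping?** Two statements might seem to.

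1. Continuous recording is stated for two periods, baseline and exercise. Product goes on between them, so a sensor could be lifted in that interval without contradicting the statement.
2. The word for immediacy in "and immediately begin a 30-minute walk on a treadmill" links chamber entry to walking. It sets no limit on the time between application and entry.

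So the text neither describes lifting nor rules it out. A statement that no site receives product would be an inference from silence.

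**What each way of filling the gap does to the comparison of conditions.**

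- *Product over or around the sensor, at both visits.* The sensed patch is untreated in both conditions. The paired difference estimates the response of skin beside the application area, including any reflex or whole-body response.
- *Sensor lifted and re-taped over product, at both visits.* The paired difference concerns treated skin. The change of placement occurs in both conditions, so it adds noise. It would favour one condition only if the two products affected probe contact differently, which the documents do not address.

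Either way the contrast is valid for what is measured, provided handling does not differ by condition. The Research Plan says that experimental and control visits follow the same protocol, and the order of conditions is randomised and counterbalanced.

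**Choice of laser Doppler site.** A paired comparison in relative units makes sense only at the same site at both visits, and forearm and finger readings are not interchangeable. An analyst would keep them apart without being told.

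**The case for a change.** The strongest contrary case is that going around the sensor and re-taping it measure different things, so the choice should not be left to staff on the day. Nothing written fixes it across 12–15 participants and two visits, a few lines would do so, and a null skin result would otherwise be hard to interpret.

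Part of this stands. The site wording is loose, and the handling of product at the sensors is unwritten. A report that described these readings as coming from treated skin, without knowing that they did, would overstate them.

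It does not carry further, for two reasons. First, a reading of directly treated skin is not a stated aim. The Abstract and the Purpose and Rationale section speak of human heat regulation and perceived temperature. The rationale's remark on heat conservation goes on to rising core temperature and reduced exercise capacity, which are whole-body consequences. No section ranks blood flow or skin temperature as primary.

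Second, neither remedy is clearly better than the present text. Keeping product off a border around each sensor alters the stated application area and otherwise only relabels the readings. Lifting and re-taping gives up the only within-visit reference for a relative-unit signal, leaving raw values to be compared between visits 7 to 14 days apart. It also places two different products under the tape and probe. If they affect contact differently (an assumption), the artefact is confounded with condition.

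**Conclusion.** No change to the plan is called for. The order of steps is as described, but the conclusion that treated skin goes unmeasured rests on what the text leaves out and concerns small patches under the sensors. It affects the interpretation of two unranked measures: laser Doppler flow, with its three timed exercise readings, and skin temperature. Core temperature, heart rate, sweat rate and thermal sensation are unaffected. The paired contrast is unbiased for what is actually measured, its type I error is not altered by this point, and no loss of power can be claimed.

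This rests on three assumptions that a competent laboratory and analyst would ordinarily meet: each participant has the same site and the same handling of product at the sensors at both visits; forearm and finger flow are not pooled; and the results are described according to whether the sensed skin received product. If handling differed systematically between gel and control visits, the comparison for these two measures would be open to bias. Nothing in the documents suggests that it would.
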